1.0 Objectives

1.1 *Describe the purpose, specific aims, or objectives of this research.*

Response:

Specific Aim 1: To determine the efficacy of Brief Behavioral Treatment for Insomnia (BBTI), experimental condition, compared to Healthy Eating Program (HEP), attention control, on insomnia severity in cancer survivors with insomnia.

Specific Aim 2: To determine predictors for efficacy of BBTI.

Specific Aim 3: To evaluate BBTI implementation with a focus on characterization of the patient- and provider-level facilitators and barriers.

1.2 *State the hypotheses to be tested, if applicable.*

NOTE: A hypothesis is a specific, testable prediction about what you expect to happen in your study that corresponds with your above listed objectives.

Response:

Hypothesis 1: Participants receiving BBTI will exhibit significant and durable improvement in insomnia severity index (key variable), sleep quality, mood, and functional status and quality of life measures over HEP.

Hypothesis 2: Selective demographics (older age), disease stage (stage I), treatment-related (surgery only), mood (nondepressed) and positive beliefs about sleep (needing less than 8-hours of sleep) will predict BBTI efficacy.

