6.0 Inclusion and Exclusion Criteria

6.1 *Describe the criteria that define who will be **included** in your final study sample.*

NOTE: This may be done in bullet point fashion.

Response:

1. Age \geq 18 years of age
2. \geq 1-month from surgery and \geq 1-month from any other treatment (except for hormone treatment or maintenance targeted therapies) for stages I through III: breast, colorectal, and prostate cancers and stages I through IV: lung cancer.
3. Meet published criteria for chronic insomnia: sleep latency $>$ 30 minutes or wake after sleep onset of $>$ 30 mins for \geq 3 nights/week for at least 1-month
4. ApneaLink Screening Apnea Hyponea Index $<$ 15

5. Ability to complete data collection instruments

6.2 *Describe the criteria that define who will be **excluded** from your final study sample.*

NOTE: This may be done in bullet point fashion.

Response:

1. Other pre-existing sleep disorders except insomnia or obstructive sleep apnea who are CPAP-compliant => 4-hours/night use
2. Unstable medical or psychiatric illness, fibromyalgia, history of seizures, current substance abuse
3. Engaged in night or rotating shift work
4. Travel across two or more time zones within 1 month prior to study participation
5. Inability to complete data collection measures independently
6. Individuals with conditions affecting the non-dominant arm (use of wrist actigraph)

6.3 *Indicate specifically whether you will include any of the following special populations in your study using the checkboxes below.*

NOTE: Members of special populations may not be targeted for enrollment in your study unless you indicate this in your inclusion criteria.

Response:

Not applicable: None of the following special populations will be recruited in the current study.

- Adults unable to consent
- Individuals who are not yet adults (infants, children, teenagers)
- Pregnant women
- Prisoners

6.4 *Indicate whether you will include non-English speaking individuals in your study.*

Provide justification if you will exclude non-English speaking individuals.

*In order to meet one of the primary ethical principles of equitable selection of subjects, non-English speaking individuals may **not** be routinely excluded from research as a matter of convenience.*

In cases where the research is of therapeutic intent or is designed to investigate areas that would necessarily require certain populations who may not speak English, the researcher is required to make efforts to recruit

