17.0 Data Management and Analysis

17.1 *Describe the data analysis plan, including any statistical procedures. This section applies to both quantitative and qualitative analysis.*

Response:

Specific Aim 1. The primary analyses involve the statistical assessment of Insomnia Severity Index (ISI) at 1 month and will be based on an analysis of covariance (ANCOVA) model. In taking this approach, we fit the dependent variable as a linear function of independent variables randomized treatment assignment, patient cancer type, the interaction between treatment assignment and cancer type, and baseline ISI level. Rather than utilizing the null distribution associated with the classic F-test for overall treatment differences within the ANCOVA framework, which is dependent on the validity of distributional assumptions, an exact permutation testing approach will be utilized. The randomization mechanism at work is a crucial component in this study in that it will be used to create the randomization distribution by which statistical significance will be determined. For more on this approach see Gail, Tan, and Piantadosi (1988)(120). Reported p-values will be obtained from the permutation distributions of the test statistics based on 10,000 Monte Carlo simulations. As additional analyses, subject covariates will be included as independent variables.

The interaction of treatment group and subject covariates may also be examined in a secondary fashion in order to identify possible differential effects of treatment. The analysis of secondary outcomes will proceed in a similar fashion. All statistical tests will be two-sided and tested at a 0.05 nominal significance level.

Specific Aim 2. Standard multiple regression will be used to determine predictors of efficacious response to BBTI. Standard diagnostic plots will be used to assess model fit and transformations of variables may be considered in order to meet statistical assumptions.

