Specific Aim 3. Evaluation of BBTI implementation focused on (a) characterization of the patient- and provider-level facilitators and barriers; and (b) knowledge/skills transfer among staff nurses using focus groups with each of the implementation facilitator groups. Transcript-based analysis, the most rigorous and accurate type of qualitative analysis, will be performed on focus group data. Audio recordings of each focus group meeting will be professionally transcribed verbatim and this text will provide the data for analysis. Prior to analysis, accuracy of the transcripts will be verified by [name]. The research team (Drs. [name] and [name]) will read all data repeatedly to achieve immersion and obtain a sense of the whole(121). Then data will be read by highlighting exact words that capture key thoughts or concepts. Next, the researchers will record first impressions, thoughts and initial analysis from the data. Labels for codes will emerge as the process continues. Codes may come directly from the text and become the preliminary coding scheme. Codes will be sorted into categories, which will be used to organize and group codes into meaningful clusters. Final codes will be organized into a hierarchical structure, if possible. Findings will be used to plan for dissemination and sustainability of this intervention. The software, Nvivo, will be used to assist in data management. During years 3 and 5, we will engage implementation facilitators and submit an IRB amendment before implementing aim 3.

17.2 If applicable, provide a power analysis.

NOTE: This may not apply to certain types of studies, including chart/records reviews, survey studies, or observational studies. This question is asked to elicit whether the investigator has an adequate sample size to achieve the study objectives and justify a conclusion.

Response:

The estimate of the variability used for sample size calculations was based on previous results, which showed the standard deviation to be approximately 4.8. Calculations show a sample size of 55 per group (110 total) will allow us to detect differences as small as 3 with 90% power. Since the actual analysis to be performed is based on a model, which incorporates baseline ISI and cancer type, which will account for some of the unexplained variability in the dependent variable, these calculations may be viewed as conservative. Based on our

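### Aim 2 commits to no treatment-by-factor interaction, so factors that predict outcome in both arms could be reported as predictors of BBTI efficacy

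*Combined protocol and SAP*

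**What the plan says.** Section 1.1 sets Aim 1 as a contrast between arms: "To determine the efficacy of Brief Behavioral Treatment for Insomnia (BBTI), experimental condition, compared to Healthy Eating Program (HEP), attention control". The next aim reads "Specific Aim 2: To determine predictors for efficacy of BBTI", and nothing there gives efficacy a different meaning. Hypothesis 2 in Section 1.2 lists the expected predictors of BBTI efficacy: "Selective demographics (older age), disease stage (stage I), treatment-related (surgery only), mood (nondepressed) and positive beliefs about sleep".

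The Aim 2 analysis in Section 17.1 is two sentences. The first is "Standard multiple regression will be used to determine predictors of efficacious response to BBTI". The second covers diagnostic plots and possible transformations. The outcome, time point, arms, baseline adjustment and factor coding are not given.

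Two interaction statements appear under Aim 1. The primary ANCOVA includes treatment by cancer type, which is not a Hypothesis 2 factor. For other covariates the plan says "The interaction of treatment group and subject covariates may also be examined in a secondary fashion in order to identify possible differential effects of treatment". Section 17.2 gives power only for the Aim 1 treatment difference.

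**The concern.** A predictor of efficacy, in the sense Aim 1 gives the word, is a factor that changes the BBTI-HEP difference. A predictor of response after BBTI may be something else: younger or depressed patients, say, might have higher 1-month ISI whichever programme they receive. A BBTI-only regression would flag such a factor, and so would a both-arm regression with main effects only. Neither model contains the term that compares the factor's effect between arms.

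Followed as written, the plan could therefore report Hypothesis 2 as supported by factors that say nothing about who gains from BBTI rather than HEP. The optional sentence under Aim 1 shows that the authors know which tool detects differential effects, but Aim 2 does not commit to it.

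**Working it through.** **The plan's own figure.** Section 17.2 uses SD 4.8, a difference of 3, 90% power and 55 per group: "will allow us to detect differences as small as 3 with 90% power". The normal formula gives 2 × (4.8 × (1.960 + 1.282)/3)² = 53.8, so 54. The t-test version gives 54.8, so 55. With 30% dropout, 55/0.7 = 78.6, so 79 per group and 158 in total. The plan's numbers reproduce; none of them concerns Aim 2.

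**How often a purely prognostic factor is flagged.** From the plan: 55 completers per arm, SD 4.8, treatment effect 3, two-sided 0.05. Assumed: one continuous factor with correlation r to 1-month ISI in both arms, zero true interaction, and baseline/1-month ISI correlation ρ. Each cell is a simulation of 6,000 trials.

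| Scenario | Outcome model | BBTI only | Both arms, no interaction | Interaction test |
|---|---|---|---|---|
| r = 0.3 with baseline and 1-month ISI, ρ = 0.4 | 1-month ISI, unadjusted | 61% | 89% | 5% |
| same | baseline-adjusted | 33% | 57% | 5% |
| same | change score | 5% | 5% | 5% |
| r = 0.3 as above, ρ = 0.6 | baseline-adjusted | 21% | 36% | 6% |
| r = 0.1 with both, ρ = 0.4 | baseline-adjusted | 8% | 11% | 5% |
| r = 0.3 with 1-month ISI, unrelated to baseline, ρ = 0.4 | baseline-adjusted | 69% | 94% | 5% |
| same | change score | 53% | 82% | 5% |

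The BBTI-only figures can be checked by hand.

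- Second row: the partial correlation given baseline is (0.3 − 0.3 × 0.4)/√((1 − 0.09)(1 − 0.16)) = 0.18/0.874 = 0.206. The expected t is 0.206 × √52/√(1 − 0.042) = 1.52 against a critical value of 2.01, so Φ(−0.49) ≈ 31%.
- Factor unrelated to baseline, adjusted: 0.3/√0.84 = 0.327, expected t 2.50, Φ(0.49) ≈ 69%.
- Change score, first scenario: the factor's correlations with baseline and follow-up cancel (0.3 − 0.3 = 0), which leaves the nominal 5%.

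With five factors in one baseline-adjusted regression, of which one is prognostic (r = 0.3, ρ = 0.4), that factor is flagged in 31% of trials (BBTI only) or 54% (both arms, no interaction).

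**What the interaction test can deliver.** For a binary factor with prevalence p and n per arm, SE = SD × √(2 × (1/(np) + 1/(n(1 − p)))). At p = 0.5 and n = 55 this is SD × √(4/27.5). Section 17.2 expects adjustment to reduce the variance ("which will account for some of the unexplained variability in the dependent variable, these calculations may be viewed as conservative"), so the adjusted SD is 4.8 × √(1 − ρ²).

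| | Unadjusted | ρ = 0.4 | ρ = 0.6 |
|---|---|---|---|
| SD | 4.80 | 4.40 | 3.84 |
| SE of interaction, 50/50 factor | 1.83 | 1.68 | 1.46 |
| Power for a 3-point interaction | 37% | 43% | 54% |
| Detectable with 80% power (2.802 × SE) | 5.1 | 4.7 | 4.1 |
| Same at alpha 0.01 (first Holm step) | 6.3 | 5.7 | 5.0 |
| 95% CI half-width | 3.6 | 3.3 | 2.9 |
| Detectable with 80% power, 20% prevalence | 6.4 | 5.9 | 5.1 |

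For 90% power on a 3-point interaction with a 50/50 factor, the requirement is four times the main-effect size: 4 × 54 = 216 per arm, against 55. Five independent tests at 0.05 would give 1 − 0.95⁵ = 23% chance of at least one false positive. In simulation, five one-at-a-time interaction models gave 22% without correction and 5% with Holm.

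**The case against.** The strongest reply is that Aim 2 asks only who does well after receiving BBTI. The method speaks of response to BBTI, and a regression in the BBTI arm answers that question. On this reading the percentages above are ordinary power to find a real prognostic factor, and no analysis is wrong. That the Aim 1 meaning of efficacy carries into Aim 2 is an inference, though the natural one, since neither Aim 2 nor Hypothesis 2 redefines the word. The reply stands as a possible intent, but it does not remove the problem: Aim 2 and Hypothesis 2 would then claim more than the regression can show, and their wording would need to change.

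Second, the plan already allows treatment-by-covariate interactions, all five factors come from baseline instruments, and multiple regression does not exclude an interaction term. That is true, but the sentence is discretionary, names no covariate and is not linked to Hypothesis 2.

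Third, the numbers are illustrative. No correlation comes from the documents, and the BBTI-only rates run from 5% to 69%. The both-arm, main-effects reading is also the less natural one, because HEP participants do not receive BBTI. Both points are fair. The BBTI-only column is the one to weigh, and no single rate should be quoted as the trial's error rate. The spread arises partly because Aim 2 leaves the outcome and baseline adjustment open.

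**Conclusion.** The concern holds and should be fixed before analysis. Aim 2 and Hypothesis 2 claim predictors of efficacy, while the committed method can show only predictors of outcome. On the natural BBTI-only reading with baseline adjustment, a factor that does not modify the BBTI effect would be flagged in about 8% to 33% of trials when it is equally correlated with baseline and 1-month ISI (r of 0.1 to 0.3, ρ of 0.4). The rate is about 69% when the factor (r = 0.3) is unrelated to baseline ISI, and a change score can bring it down to 5%. These rates rest on assumed correlations and 55 completers per arm. That only the interaction contrast isolates effect modification does not depend on those assumptions. The primary 1-month ISI analysis is not affected.

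**What to change.** Choose one option and write it into Section 17.1.

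**Option A, keep the efficacy claim.** State that Hypothesis 2 will be judged on treatment-by-factor interaction estimates with 95% confidence intervals for the five named factors: age, stage, surgery only, HADS depression and the DBAS sleep-need belief. Use both randomized arms and a model of 1-month ISI adjusted for baseline ISI and cancer type. Cancer type belongs in the model because the eligible stages differ by type (Section 6.1: stages I to III for three of the cancers, but "breast, colorectal, and prostate cancers and stages I through IV: lung cancer"). Factors may be fitted one at a time. Fix the coding and multiplicity handling in advance; Holm over five is one choice. Label any BBTI-only regression as descriptive prognosis within BBTI, not as evidence for Hypothesis 2.

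**Option B, keep the within-BBTI analysis.** Reword Aim 2 and Hypothesis 2 as predictors of outcome among participants receiving BBTI, and state the outcome and baseline adjustment.

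Option B costs wording only. Option A costs wording and five small models on data already collected. Its drawback is the imprecision shown above: power for a 3-point interaction is only 37% to 54%, before any loss from factors correlated with cancer type. A null result would not refute Hypothesis 2, so the estimates and intervals should carry the report, labelled exploratory.

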18.0 Confidentiality

A. Confidentiality of Study Data

Describe the local procedures for maintenance of confidentiality of study data and any records that will be reviewed for data collection.

18.1 A. Where and how will all data and records be stored? Include information about: password protection, encryption, physical controls, authorization of access, and separation of identifiers and data, as applicable. Include physical (e.g. paper) and electronic files.

Response:

Research materials will be stored in a locked office in either a locked file cabinet or a password-protected computer system. Consent forms with participant identifiers are stored in separate files from de-identified paper data. An excel spreadsheet with screened positive individuals will be kept on a password protected computer file on Roswell Park Cancer Center's Sharepoint Server.

18.2 A. How long will the data be stored?

Response:

Records will be stored for a period of at least 5 years following study completion. At the end of data collection excel screening excel spreadsheet will be deleted by Roswell's IT.

18.3 A. Who will have access to the data?

Response:

Only the PI and members of the research team will have access to the data and excel screening spreadsheet.

18.4 A. Who is responsible for receipt or transmission of the data?

Response:

The PI and members of the research team are responsible for the receipt and transmission of the data.

18.5 A. How will the data be transported?

Response:

The investigator performing the visit will transport the data securely in a briefcase.

B. Confidentiality of Study Specimens

Describe the local procedures for maintenance of confidentiality of study specimens.

N/A: No specimens will be collected or analyzed in this research.
(Skip to Section 19.0)

18.6 B. Where and how will all specimens be stored? Include information about: physical controls, authorization of access, and labeling of specimens, as applicable.

Response:

Not Applicable: No Specimens will be collected or analyzed in this research.

18.7 B. How long will the specimens be stored?

Response:

Not Applicable: No Specimens will be collected or analyzed in this research.

18.8 B. Who will have access to the specimens?

Response:

Not Applicable: No Specimens will be collected or analyzed in this research.

18.9 B. Who is responsible for receipt or transmission of the specimens?

Response:

Not Applicable: No Specimens will be collected or analyzed in this research.

18.10 B. How will the specimens be transported?

Response:

Not Applicable: No Specimens will be collected or analyzed in this research.

19.0 Provisions to Monitor the Data to Ensure the Safety of Subjects

- N/A:** This study is not enrolling subjects, or is limited to records review procedures only. This section does not apply.

NOTE: Minimal risk studies may be required to monitor subject safety if the research procedures include procedures that present unique risks to subjects that require monitoring. Some examples include: exercising to exertion, or instruments that elicit suicidality or substance abuse behavior. In such cases, N/A is not an acceptable response.

19.1 Describe the plan to periodically evaluate the data collected regarding both harms and benefits to determine whether subjects remain safe.

Response:

The PI will be responsible for ensuring data integrity and safety monitoring for human subjects and communicating any negative outcomes or any serious events to the IRBs and other offices/agencies. Because of the minimal to low risk associated with this protocol, the data safety and monitoring plan (DSMP) for this project involves a Safety Monitoring Committee (SMC). The SMC will ensure participant safety, ensure the validity and integrity of the data, monitor study progress, and make recommendations regarding appropriate protocol and operational changes which may have substantial effects upon the ultimate interpretation of the study. They will also be responsible for promptly report any serious adverse events to the Institutional Review Boards (IRB) at Roswell Park Cancer Institute and the University at Buffalo.

Weekly reviews of participant accrual will be conducted by the PI during weekly research meetings. If participant accrual and/or retention drop below what is required for successful completion of this study, the PI will alert the statistician and strategies will be developed to overcome the identified problems. Records from subjects recruited during that week will also be scrutinized to insure that all participants are eligible for participation in the study. The PI and members of the research team will be monitoring developments in the literature and results of related studies that may have an impact on the safety of participants or on the ethics for the research study.

19.2 Describe what data are reviewed, including safety data, untoward events, and efficacy data.

Response:

Data review includes eligibility, referral for sleep apnea, referral for low oxygen during sleep, completion of data collection instruments, adherence to intervention, number of follow up phone calls accepted, and outcome measures of efficacy:

sleep, mood, functional status and quality of life. Daytime sleepiness will also be evaluated daily, but monitored weekly. Additionally, as previously mentioned, we are adding a 6 and 9 month follow up email to check on participants' safety. If participants report that they are excessively sleepy, we will provide recommendations to reduce sleepiness by telephone or email.

Because of the minimal to low risk associated with this protocol there are no life-threatening anticipated adverse events for this proposed research project. In the event of an unanticipated adverse event, such as disease-related patient death, it will be reported to and reviewed by the PI, SMC, and referring physician within seven days. Next, the IRBs at Roswell Park Comprehensive Cancer Center and the University at Buffalo as well as sponsoring agencies (NINR) will be notified within 15 days. A thorough investigation will be initiated, including review of the protocol to insure no undue exposure to risk occurred.

19.3 Describe any safety endpoints.

Response:

This low risk intervention may lead to emotional distress in participants who may become frustrated if insomnia does not improve. Anxiety and depression will be assessed at baseline, one, three and 12-months post-intervention. Scores greater than seven on either scale will be communicated to participants who will be encouraged to contact their health care provider for follow up care.

19.4 Describe how the safety information will be collected (e.g., with case report forms, at study visits, by telephone calls with participants).

Response:

The safety information will be collected with self-report surveys, during study visits and by telephone calls with participants.

19.5 Describe the frequency of safety data collection.

Response:

Safety data collection occurs at baseline, weekly then at 1-month, 3-months and 12 months post-intervention.

19.6 Describe who will review the safety data.

Response:

The PI, study coordinator, research assistant and members of the Safety Monitoring Committee.

19.7 Describe the frequency or periodicity of review of cumulative safety data.

Response:

Reviews of cumulative safety data will initially occur weekly, then biweekly and eventually monthly.

19.8 Describe the statistical tests for analyzing the safety data to determine whether harm is occurring.

Response:

Hospital Anxiety and Depression Scale scores will be summarized.

19.9 Describe any conditions that trigger an immediate suspension of the research.

Response:

We do not anticipate any condition that would trigger an immediate suspension of the research.

